5.2 Confidentiality

All data and records generated during the process of this study will remain confidential in accordance with all Institutional and HIPAA policies on subject privacy. All documents will be used by the Investigator and other personnel solely for the purposes of this study. All safeguards to maintain subject confidentiality are described above (5.1 Data Collection and Management). No information will leave Montefiore in the event that an investigator leaves during the duration of the study.

5.3 Regulatory and Ethical Considerations

5.3.1 Risk assessment

Stretta is a safe, non-invasive FDA approved procedure performed endoscopically under moderate sedation or general anesthesia which uses radio frequency (RF) energy applied to the lower esophagus over 14 minutes per a specific FDA approved protocol and procedure.

Definition and Reporting of Serious Adverse Events (SAEs)

A serious adverse event (SAE) is a subtype of adverse event. An SAE is any adverse event occurring when the subject outcome is:

- Death
- Life-threatening (i.e., subject was at substantial risk of dying at the time of the AE)
- Inpatient hospitalization or prolongation of existing hospitalization
- Disability or permanent damage
- Other serious medical events that jeopardize the health of the subject and require medical or surgical intervention such as bronchospasm, blood dyscrasias, seizures/convulsions, or development of drug dependency or drug abuse.

The principal investigator or designee must comply with applicable local regulatory authority and IRB/IEC requirements concerning the reporting of SAEs and any safety-related documentation (e.g.., safety letters, revised IB) that may be received from the sponsoring entity. Additionally, the principal investigator will keep safety-related documentation in secured site files.

5.3.2 Potential Benefits of Study Participation

Full resolution or improvement in symptoms related to GERD

5.3.3 Risk-benefit assessment

Patients will be undergoing a procedure that is FDA approved and is an acceptable treatment for GERD. This study is intended to collect data and outcomes in the bariatric population.

5.4 Informed consent

Informed will be obtained from the subjects directly and not through a health care proxy. Qualified interpreter services will be used when appropriate. All risks, benefits, and alternatives of the procedure with be explained in detail by study to the participants and supplemental documentation will be provided to patients for further review.

A copy of the Informed Consent document is provided in Appendix 3

5.5 Payment to subjects/families

No monetary payment will be given to participants.

6. Statistical Considerations

6.1 Statistical Methods

Data will be entered on an excel spreadsheet and analyzed with SAS v9.3. Data analysis will be preceded by quality control of our data which will include checks for accuracy, completeness and internal validity. Rates of achievement of 50% reduction of symptoms will be computed and reported with their 95% confidence intervals. Descriptive data analysis will be conducted and all adverse events and overall patient characteristics will be described. The distribution of change in symptom scores will be examined and the decrease in patient symptoms will also be examined and described. If the distribution of this score approximates normality, symptom reduction will be described using mean and standard deviation. Otherwise we will use median and interquartile ranges. Bivariate analysis will be conducted to examine factors associated with achievement of 50% reduction in symptoms. Categorical variables will be analyzed using the Chi-Square's exact test. Continuous variables whose distribution meets normality assumptions will be analyzed with the t-test. Variables whose distribution does not approximate normality will be analyzed using the Wilcoxon rank sum test. While we recognize that the sample size is modest – an exploratory multivariate logistic regression analysis will be conducted to examine factors associated with 50% symptom reduction

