3.2 Criteria For Evaluation

3.2.1 Primary Endpoint

• Primary endpoint will be based RSI and HQRL indices and will be a determination of whether the patient achieved at least a 50% reduction in symptoms at the 6 12 and 24 month points as compared to baseline.

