6.2 Sample Size and Power

The target number of patients proposed for this protocol is based on our primary objective of estimating the proportion of patients achieving at least a 50% reduction of symptoms from baseline as measured by RSI and HQRL indices 1 year post treatment. Sample size calculations are based on this primary objective. Our target sample size is 80 unless perforation occurs in more than 2 patients or more than one death directly related to Stretta procedure or the accrual is terminated during interim analysis. A sample size of 50 would produce a two-sided 95% confidence interval with a width of 0.289 for a proportion of 0.5 and a width of 0.267 for proportions of 0.7. Taking into consideration that given improvement of symptoms or other factorswe estimate a 30% patientsdropout prior to completing the 24 month follow-upwe will increase target sample size to a total of 80 patients

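### Candidate factors are tested only against the yes/no 50% reduction; section 6.1 should add a baseline-adjusted model of the RSI and GERD-HRQL scores

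*Combined protocol and SAP*

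**What the plan says.** Section 6.1 (Statistical Methods) has three layers.

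- **Primary result.** The proportion achieving the 50% reduction is reported with its 95% CI. Section 3.2.1 defines this per patient as "whether the patient achieved at least a 50% reduction in symptoms at the 6 12 and 24 month points as compared to baseline".
- **Scores.** "The distribution of change in symptom scores will be examined and the decrease in patient symptoms will also be examined and described". The summary is mean and SD, or median and interquartile range. No model or test of the score is planned.
- **Factors.** "Bivariate analysis will be conducted to examine factors associated with achievement of 50% reduction in symptoms". Categorical factors get an exact form of the chi-square test; continuous factors get a t-test or Wilcoxon rank sum test. Then, prefaced by "While we recognize that the sample size is modest", the plan adds that "an exploratory multivariate logistic regression analysis will be conducted to examine factors associated with 50% symptom reduction".

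The factors are neither named nor counted, and the baseline score is not mentioned as a covariate. Section 4.3 has both questionnaires completed off medication at baseline, 6, 12 and 24 months, so the numeric scores will be available.

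Section 6.2 sizes the study for the precision of one proportion at 1 year: "A sample size of 50 would produce a two-sided 95% confidence interval with a width of 0.289 for a proportion of 0.5". If the true rate is 0.7, the stated figure is 0.267. The plan raises 50 to 80 for 30% dropout before the end of 24-month follow-up. No factor analysis is sized.

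**The concern.** Each patient supplies a numeric score at baseline and at follow-up, but every planned test of a factor first reduces the pair to yes or no. A patient who improves by 51% counts the same as one who improves by 95%, and differently from one who improves by 49%. In a study of this size that is a costly loss.

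Defining response relative to baseline is also not the same as adjusting for baseline. The chance of crossing the threshold can still depend on the starting score, so a factor linked to baseline severity can appear to predict benefit when it does not.

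The factor analyses matter to the study's aims. Section 2.2 asks about gastric emptying and its link with GERD, and section 3.2.2 lists gastric dysmotility as a contributory factor. Section 6.1 gives no other inferential method for such questions.

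**Working it through.** **1. The plan's own figures.** Exact (Clopper-Pearson) 95% intervals with n = 50:
- 25/50: 0.3553 to 0.6447, width 0.289.
- 35/50: 0.5539 to 0.8214, width 0.267.

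Both match section 6.2. For dropout, 50/0.70 = 71.4, so 72 would do; the stated 80 is conservative.

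**2. How many patients are scored.** At 24 months, 80 × 0.70 = 56. The sample-size objective is at 1 year and no 12-month dropout is given. If dropout follows the plan, the 12-month number lies between 56 and 80. The figure of 50 is the precision target, not an expected count.

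**3. Information kept by the cut.** For a normal score cut so that a proportion p respond, relative efficiency = φ(z_p)² / [p(1−p)].
- p = 0.5: 0.3989² / 0.25 = 0.64.
- p = 0.7: 0.3477² / 0.21 = 0.58.

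So 56 patients are worth about 36 or 32, and 80 are worth about 51 or 46.

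**4. Power, illustrative.** Assumptions (none in the documents): normal scores, baseline mean 28 SD 9, follow-up mean 14 SD 9, correlation 0.4, two equal factor groups differing by 5 points at follow-up, two-sided 5%. These imply about 50% response.

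*Baseline-adjusted linear model.* Residual SD = 9 × √(1 − 0.4²) = 8.25.
- n = 56: SE = 2 × 8.25/√56 = 2.20; 5/2.20 = 2.27; power about 60%.
- n = 80: SE = 1.84; 5/1.84 = 2.71; power about 76% by formula, 74% simulated.

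*Yes/no outcome.* Response means follow-up − 0.5 × baseline ≤ 0. This margin has SD = 9 × √(1 + 0.25 − 0.4) = 8.30. With the 5 points split evenly, response rates are Φ(±2.5/8.30) = 0.62 and 0.38. For a chi-square test with 28 per group, power = Φ[(0.237 − 1.96 × 0.134)/0.130], about 42%.

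Simulated power, in line with these formulas:

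| Patients | Effect | Exact test | Uncorrected chi-square | Linear model with baseline |
|---|---|---|---|---|
| 56 | 5 points | 33% | 43% | 60% |
| 56 | 7 points | 58% | 68% | 86% |
| 80 | 5 points | 48% | 58% | 74% |

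Repeat runs differ by up to about 3 points. With no effect, at 56 patients, the exact test rejects in about 2.5–3% of trials and the other two in about 5%. For a continuous factor, where section 6.1 plans a t-test or Wilcoxon test, the gap is about 17–19 points at 56 patients.

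**5. Dependence on baseline.** Under the same assumptions the expected margin at baseline b is 14 + 0.4(b − 28) − 0.5b = 2.8 − 0.1b. At b = 18 it is +1.0, so response is Φ(−1.0/8.25) = 45%. At b = 38 it is −1.0, so response is 55%. No factor is acting in either case.

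**6. An unadjusted change score would not do instead.** Its SD is 9 × √(2 − 0.8) = 9.86. With n = 56, SE = 2.64, 5/2.64 = 1.90, and power is Φ(1.90 − 1.96), about 47–48%. Most of the gain is lost without the baseline covariate.

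**7. Logistic model.** Smaller outcome group, at the conventional 10 outcomes per predictor:
- 56 patients: 28 at 50% response (2 predictors); 16.8 at 70% (1 predictor).
- 80 patients: 40 at 50% response (4 predictors); 24 at 70% (2 predictors).

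**The case against.** The study is sized to estimate one proportion, and nothing here touches that estimate or its CI. The authors acknowledge the modest sample and label the regression exploratory. Testing factors against the declared endpoint keeps the two aligned, and a model in score points answers a somewhat different question. All of this stands. It argues for keeping the responder analyses and adding to them, not for leaving the scores unmodelled. The exploratory label is attached to the regression, not to the bivariate tests.

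The exact-test comparison also overstates what the cut costs. At 56 patients, 10 of the 27 points between 33% and 60% come from the exact test's conservatism; the other 17 remain with an uncorrected chi-square test. The planned exact test is also not the one used for continuous factors. These limits are accepted, and the figures above show them separately.

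A reader might infer three stronger things that the documents do not support.

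- **That there are too few outcomes for the logistic model.** Section 6.1 gives no number of predictors, so this cannot be shown. Ten outcomes per predictor is a convention, and a model within the limits in step 7 would meet it.
- **That baseline is excluded.** It is only unstated, and could be among the unnamed factors.
- **That real predictors will be missed.** The calculation shows lower power, not certain failure.

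**Conclusion.** The point holds as a matter of efficiency in the secondary, exploratory analyses. Every inferential factor analysis uses the dichotomised outcome, the numeric scores are only described, and no baseline adjustment is stated. Under a normal-score assumption the cut discards about 36–42% of the information. Under the illustrative assumptions, a 5-point effect loses 16–17 points of power against an uncorrected chi-square test and 26–27 points against the planned exact test, over the range of 56 to 80 patients.

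The size depends on score distributions, correlation and effect sizes that the documents do not give. A higher baseline–follow-up correlation raises the power of the adjusted model; marked skewness would change the figures. Some loss from dichotomising is seen at both ends of the 56–80 range. The primary endpoint and the sample size are not in question.

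**What to change.** Keep the 50% responder rate with its 95% CI as the primary endpoint. Add to section 6.1, as the main exploratory factor analysis, a linear model of the 12-month score on the factor of interest with the baseline score as covariate. Fit it separately for RSI and GERD-HRQL and report each factor effect with its 95% CI. Model the 12-month score, or the change score with baseline included; do not use the unadjusted change. Retain the responder-based bivariate tests and logistic regression as supporting analyses. Note beside the regression that, at 10 outcomes per predictor, it would support about 1–2 predictors with 56 patients and 2–4 with 80, at response rates of 70% to 50%.

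The cost is SAP wording only: section 4.3 already collects the scores, and no patients or visits are added. The downside is that factor effects are expressed in score points rather than odds of response, which is why the responder analyses should remain alongside.

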6.2 Sample Size and Power

The target number of patients proposed for this protocol is based on our primary objective of estimating the proportion of patients achieving at least a 50% reduction of symptoms from baseline as measured by RSI and HQRL indices 1 year post treatment. Sample size calculations are based on this primary objective. Our target sample size is 80 unless perforation occurs in more than 2 patients or more than one death directly related to Stretta procedure or the accrual is terminated during interim analysis. A sample size of 50 would produce a two-sided 95% confidence interval with a width of 0.289 for a proportion of 0.5 and a width of 0.267 for proportions of 0.7. Taking into consideration that given improvement of symptoms or other factorswe estimate a 30% patientsdropout prior to completing the 24 month follow-upwe will increase target sample size to a total of 80 patients

6.3 Patient Accrual

Patient accrual will begin shortly after approval of protocol at a rate of approximately 10 to 15 patients per month and estimate patient accrual will be completed 6 months after start of protocol

6.4 Interim analysis and stopping rules:

While Stretta has been extensively used safely, we will consider perforation in more than 2 patients or more than 1 deaths directly related to Stretta procedure as unacceptable since this rate is higher than one would expect from invasive esophageal junction intervention such as dilation. Interim analysis will be conducted in an ongoing manner after treatment of eachand every patient, by the principal investigator and the lead investigator at each site. If more than 1 patientdiesor more than 2 patients suffer perforation attributable to the treatment, we will stop enrolment if no critical adverse events occur we will continue accrual to the target sample size of 80 patients. If a patient suffers a morbid event such as perforation or other life threatening event or event that requires surgical intervention accrual will be suspend and a through investigation be conducted. After the root cause is determined the study team will confer with the IRB and made a determination as to whether to resume accrual. If there is any event or evidence of increased morbidity form the treatment with the device the manufacturer FDA safety information and adverse event program (Medwatch) will be notified.

7. Publication

Once the study is complete and significant conclusions are made, a manuscript will be submitted to a relevant journal for publication.

- [3] Rosenthal RJ, Panel ISGE. International Sleeve Gastrectomy Expert Panel Consensus Statement: best practice guidelines based on experience of > 12,000 cases. Soard 2012;8:8–19.

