1.2 Compliance Statement

This study will be conducted in full accordance of all applicable Montefiore Medical Center Research Policies and Procedures and all applicable Federal and state laws and regulations including 45 CFR 46, and the HIPAA Privacy Rule. Any episode of noncompliance will be documented.

The investigators will perform the study in accordance with this protocol, will obtain consentand assent when applicable (unless a waiver is granted), and will report unexpected problems in accordance with The Montefiore Medical Center IRB Policies and Procedures and all federal requirements. Collection, recording, and reporting of data will be accurate and will ensure the privacy, health, and welfare of research subjects during and after the study.

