3.1.3 Enrollment

Patients may be enrolled prospectively or retrospectively up to 6 months following Stretta procedure.

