3.2.4 Exclusion Criteria

- 1. Age < 18 or > 80
- 2. History of a severe psychiatric disorder: including suicidal ideation, or admission to a psychiatric institution.
- 3. Unable or unwilling to consent for an invasive procedure.

- 4. History of intestinal leak after surgery.
- 5. History of revisional bariatric surgery
- 6. Significant sleeve abnormalities such and twist or large fundus
- 7. Hiatal hernia(>2cm)
- 8. Pregnancy
- 9. Inability to comply with study protocols and procedures
- 10. Esophageal stricture, Eosinophilic Esophagitis or Achalasia
- 11. Prior esophageal surgery or therapy for Barrett's Esophagus
- 12. Grades 3 or 4 esophagitis
- 13. Gastric or esophageal varices
- 14. History of obstruction of the small bowel or inflammatory bowel disease
- 15. Pacemaker or implanted cardiac defibrillator
- 16. Coagulopathy or use of anticoagulants
- 17. ASA classification >3
- 18. Scleroderma or other connective diseases
- 19. Use of imunosuppressive medications.

4. Study Procedures

A Schedule of Events representing the required testing procedures to be performed for the duration of the study is diagrammed in Appendix 1.

A description of the assessment and work-up to be performed on the initial evaluation, pre-procedure testing, and each of the post-procedural follow-ups is provided in Appendix 2.

Prior to conducting any study-related activities, written informed consent and the Health Insurance Portability and Accountability Act (HIPAA) authorization must be signed and dated by the subject.

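### A Stretta-related death before retrospective consent cannot enter the study, yet surviving retrospective entrants count toward the 80 patients behind the stopping rule and the safety description

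*Combined protocol and SAP*

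**What the plan says.** Section 3.1.3 opens two entry routes: "Patients may be enrolled prospectively or retrospectively up to 6 months following Stretta procedure". No visible section caps the retrospective share.

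The opening text of section 4 requires that, before any study activity, written consent and HIPAA authorization "must be signed and dated by the subject". Section 5.4 adds that consent is "obtained from the subjects directly and not through a health care proxy". Section 1.2 has a general exception, "unless a waiver is granted", but no visible section applies it to deceased or retrospectively entered patients.

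On stopping, section 6.4 states: "we will consider perforation in more than 2 patients or more than 1 deaths directly related to Stretta procedure as unacceptable". It then says enrolment ends if more than one patient dies or "more than 2 patients suffer perforation attributable to the treatment, we will stop enrolment". Safety is to be reviewed after each patient is treated. Section 6.2 ties the same limits to the enrolment target: "Our target sample size is 80 unless perforation occurs in more than 2 patients or more than one death directly related to Stretta procedure". Neither section distinguishes the two entry routes.

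Section 6.1 plans rates with 95% confidence intervals only for the 50% symptom reduction. Adverse events are to be described.

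**The concern.** A patient has to be alive and able to sign in order to enter retrospectively. Anyone who dies of the procedure between treatment and that signature is never a study patient, while those who survive can be enrolled and fill places among the 80. For retrospective entrants the number of deaths before entry is zero by construction, whatever the true risk. This differs from ordinary selection: a site that enrolled every eligible survivor would still record no pre-entry deaths. For these patients the review after each treatment also cannot take place at the time of treatment, because they are not yet in the study.

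Two things are at stake. The death limb of the rule has fewer patients in whom an early death could be seen than the 80 suggests. And a safety summary over all enrolled patients leaves pre-entry deaths out of the numerator while keeping the survivors in the denominator, so it leans toward safe. Section 1.1 says there are no previous studies of Stretta for reflux after sleeve gastrectomy, so readers may take their safety evidence for this population from this cohort.

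**Working it through.** **Inputs from the documents.** Target of 80 (sections 6.2 and 6.4); the death limb is met at 2 or more and the perforation limb at 3 or more (section 6.4); retrospective entry up to 6 months after treatment (section 3.1.3); the subject's own consent (sections 4 and 5.4).

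**Assumed inputs.** The true death rate *p*, the number *m* of the 80 observed from treatment, and the share *q* of related deaths that precede retrospective entry. The documents give none of these, so ranges are shown. The value 2.5% is 2/80, the trigger count over the target; it is not a rate that the plan assumes.

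**The plan's own figures.** Section 6.2 gives interval widths of 0.289 and 0.267 at n = 50. Exact (Clopper-Pearson) intervals for 25/50 and 35/50 have widths 0.2895 and 0.2675, which agree. Wald intervals give 0.277 and 0.254, which do not. The plan's precision figures are therefore exact ones, and exact limits are used below. The documents give no operating characteristics for the stopping rule, so there is nothing to reproduce there.

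**Step 1: all related deaths precede retrospective entry (q = 1).** Only the *m* patients observed from treatment can contribute a death:

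P(2 or more) = 1 − (1−p)^m − m·p·(1−p)^(m−1)

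- p = 0.025, m = 80: 1 − 0.132 − 0.271 = 0.597
- p = 0.025, m = 40: 1 − 0.363 − 0.373 = 0.264

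Expected visible deaths fall from 80 × 0.025 = 2.0 to 40 × 0.025 = 1.0, while the denominator stays at 80.

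| Assumed death rate | m = 80 | m = 60 | m = 40 | m = 20 |
|---|---|---|---|---|
| 1% | 0.191 | 0.121 | 0.061 | 0.017 |
| 2.5% | 0.597 | 0.444 | 0.264 | 0.088 |
| 5% | 0.914 | 0.808 | 0.601 | 0.264 |

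**Step 2: only some deaths precede entry.** Take 40 prospective patients at rate p. For the 40 retrospective entrants, the chance of a related death after entry, given survival to entry, is r = p(1−q)/(1−pq). With p = 0.025 and q = 0.5, r = 0.0125/0.9875 = 0.01266.

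- P(0) = 0.975^40 × 0.98734^40 = 0.363 × 0.601 = 0.218
- P(1) = 40(0.025)(0.975^39)(0.98734^40) + 40(0.01266)(0.98734^39)(0.975^40) = 0.224 + 0.112 = 0.336
- P(2 or more) = 1 − 0.218 − 0.336 = 0.446

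With q = 0.9 the same calculation gives 0.302.

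**Step 3: what zero deaths would show.** The exact two-sided 95% upper limit after no events is 1 − 0.025^(1/n): 4.5% for n = 80 and 8.8% for n = 40.

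**The case against.** Several points against the concern stand and limit it.

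- A reader might infer that the rule can never register a death on the retrospective route. It can: a retrospective entrant who consents and later dies is counted, and entry may come soon after treatment because 6 months is a maximum.
- A reader might infer that perforations vanish in the same way. Someone who survives a perforation can usually consent within the window. That limb loses only fatal or incapacitating cases, or cases lost through selective entry.
- Section 6.1 plans no death rate, only a description of adverse events. The bias lies in any safety summary made over all enrolled patients, not in a named planned statistic.
- A reader might infer that the study could run to completion despite clear harm. The documents do not support that. Under section 6.4 a single perforation, life-threatening event or event needing surgery pauses accrual for investigation and discussion with the IRB, and signs of increased morbidity are reported to MedWatch. Section 5.1 adds three-monthly data review and IRB reporting of unanticipated risks, which is not limited to enrolled subjects. None of these expressly counts pre-entry deaths, but they are real safeguards.
- Section 6.4 speaks of patients without saying enrolled patients, so a wider count might be meant. No visible section, however, asks sites to log treated patients who never enrol.
- A mostly retrospective cohort fits poorly with a study described as prospective that requires a pre-procedure workup. And if deaths are rare the limb seldom fires anyway: at an assumed 0.5% it does so with probability 0.061 even with all 80 observed.

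The mechanism survives all of this. What these points restrict is its reach and its likely size.

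**Conclusion.** The point holds in a limited form. Read together, sections 3.1.3, 4, 5.4 and 6.4 make a Stretta-related death before retrospective consent unobservable to the study, while retrospective survivors count toward the 80. A safety description over all enrolled patients therefore leans toward safe, and the death limb of the rule rests on fewer patients than it appears to.

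The size cannot be fixed from the documents. With half the patients retrospective and an assumed 2.5% death rate, the chance of meeting the death limb is between 0.26 (all related deaths precede entry) and about 0.45 (half do), against 0.60 with everyone observed from treatment. With a small retrospective share the effect is small; with none it disappears. The zero-event limits (4.5% on 80, 8.8% on 40) show how far a statement over the full 80 could overstate the evidence on procedural deaths. The matter should be corrected, but it does not by itself invalidate the safety oversight.

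**What to change.** In section 6.1, calculate procedural death and perforation proportions, with exact 95% confidence intervals, only in patients who consented before Stretta. List events in retrospective entrants separately, outside that denominator, and report how many patients entered by each route.

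Reconcile sections 3.1.3, 5.4, 6.2 and 6.4 so that section 6.4 states which patients its counts refer to, given that early deaths are not observable in retrospective entrants. No change of threshold is proposed.

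The cost is a few sentences and wider intervals from a smaller denominator; no extra patients or procedures are needed.

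A tempting alternative is to apply the existing limits to a site tally of every post-sleeve patient treated since site opening. That would change how the rule behaves. At an assumed 1% perforation risk, the chance of three or more perforations is 0.047 in 80 patients but 0.32 to 0.58 in an assumed 200 to 300 (the 10 to 15 centres at 20 each in section 3.1.1). It would also miss patients treated before a site opened who could still enter retrospectively.
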